## **8.7 ADMINISTRATIVE STRUCTURE OF THE TRIAL**

The trial is sponsored by Boehringer Ingelheim (BI).

The trial will be conducted at

, under the supervision of the Principal Investigator. Relevant documentation on the participating (Principal) Investigators (e.g. their curricula vitae) will be filed in the ISF.

BI has appointed a Clinical Trial Leader, responsible for coordinating all required trial activities, in order to

- Manage the trial in accordance with applicable regulations and internal SOPs
- Direct the clinical trial team in the preparation, conduct, and reporting of the trial
- ensure appropriate training and information of clinical trial managers (CTM), Clinical Research Associates, and investigators of participating trial sites

The trial medication will be provided by the Clinical Trial Supplies Unit, BI Pharma GmbH & Co. KG, Biberach, Germany (BI 894416) or will be obtained by the clinical trial site from a public pharmacy (rifampicin).

Safety laboratory tests will be performed by the local laboratory of the trial site ).

Analysis of BI 894416 concentrations in plasma and urine will be performed at ,

Analysis of rifampicin concentrations in plasma will be performed at

On-site monitoring will be performed by BI or a contract research organisation appointed by BI.

Data management and statistical evaluation will be done by BI or a contract research organization appointed by BI according to BI SOPs.

Tasks and functions assigned in order to organise, manage, and evaluate the trial are defined according to BI SOPs. A list of responsible persons and relevant local information can be found in the ISF.

## **10. APPENDICES**

Not applicable.

Proprietary confidential information © 2019 Boehringer Ingelheim International GmbH or one or more of its affiliated companies

## 11. DESCRIPTION OF GLOBAL AMENDMENT(S)

### 11.1 GLOBAL AMENDMENT (REVISED PROTOCOL)

Revised Protocol, due to first submission to BfArM and ethic committee.

Date of amendment (revision)	21 June 2019
EudraCT number	2019-000507-33
EU number	
BI Trial number	1371-0005
BI Investigational Medicinal Product(s)	BI 894416
Title of protocol	Effect of rifampicin on the pharmacokinetics of a single oral dose of BI 894416 in healthy male subjects (an open-label, one-way crossover study)
CTP-version 2.0 is the first submission to IRB / IEC / Competent Authority	
To be implemented only after approval of the IRB / IEC / Competent Authorities	
To be implemented immediately in order to eliminate hazard – IRB / IEC / Competent Authority to be notified of change with request for approval	
Can be implemented without IRB / IEC / Competent Authority approval as changes involve logistical or administrative aspects only	
Section to be changed	All sections which address site specific requirements
Description of change	To be consistent with site specific requirements
Rationale for change	(1) Adaption to the local site requirements ( ); (2) Change of CTL responsibilities

Proprietary confidential information © 2019 Boehringer Ingelheim International GmbH or one or more of its affiliated companies

## 11.2 GLOBAL AMENDMENT 2

Date of amendment	26 July 2019
EudraCT number	2019-000507-33
EU number	
BI Trial number	1371-0005
BI Investigational Medicinal Product(s)	BI 894416
Title of protocol	Effect of rifampicin on the pharmacokinetics of a single oral dose of BI 894416 in healthy male subjects (an open-label, one-way crossover study)
To be implemented only after approval of the IRB / IEC / Competent Authorities	
To be implemented immediately in order to eliminate hazard – IRB / IEC / Competent Authority to be notified of change with request for approval	
Can be implemented without IRB / IEC / Competent Authority approval as changes involve logistical or administrative aspects only	
Section to be changed	4.1.3 Method of assigning subjects to treatment groups  1.2.2 Rifampicin
Description of change	4.1.3 Justification of simultaneous dosing of all subjects on day 1  1.2.2 SmPC Update March 2019 (already submitted)
Rationale for change	4.1.3 Health authority / EC request  1.2.2 Came effected during CTP-Preparation

Proprietary confidential information © 2019 Boehringer Ingelheim International GmbH or one or more of its affiliated companies

### 11.3 GLOBAL AMENDMENT 3

Date of amendment	09 September 2019
EudraCT number	2019-000507-33
EU number	
BI Trial number	1371-0005
BI Investigational Medicinal Product(s)	BI 894416
Title of protocol	Effect of rifampicin on the pharmacokinetics of a single oral dose of BI 894416 in healthy male subjects (an open-label, one-way crossover study)
To be implemented only after approval of the IRB / IEC / Competent Authorities	
To be implemented immediately in order to eliminate hazard – IRB / IEC / Competent Authority to be notified of change with request for approval	
Can be implemented without IRB / IEC / Competent Authority approval as changes involve logistical or administrative aspects only	
Section to be changed	Title page Flow chart 5.2.3 Safety laboratory parameters 5.3.2.1 Blood sampling for pharmacokinetic analysis
Description of change	Title page: - Department of TMCP was deleted Flow chart: - Footnote 5 was corrected to 10 - Cotinine test was added to screening examination in footnote 1 5.2.3 Safety laboratory parameters: - Erythrocytes was corrected to haemoglobin 5.3.2.1 Blood sampling for pharmacokinetic analysis: - Correction of time and storage conditions for rifampicin samples
Rationale for change	Title page: Due to internal restructure of organisation Flow chart: Correction of inconsistency and typos 5.2.3: Correction of inconsistencies due to quantification method 5.3.2.1: Correction due to new stability data of rifampicin in plasma

## **2. LIST OF ABBREVIATIONS**

See Medicine Glossary:

website: glossary

Term	Definition / description
ALT	Alanine transaminase
AST	Aspartate transaminase
AUC 0-tz	Area under the concentration-time curve of the analyte in plasma over the time interval from 0 to the last quantifiable data point
AUC 0-∞	Area under the concentration-time curve of the analyte in plasma over the time interval from 0 extrapolated to infinity
BMI	Body mass index
BWU	Bioavailability/Bioequivalence, Within-Subject Design, uncontrolled
CI	Confidence interval
C max	Maximum measured concentration of the analyte in plasma
CV	Arithmetic coefficient of variation
DBLM	Database lock meeting
DILI	Drug induced liver injury
gCV	Geometric coefficient of variation
gMean	Geometric mean
LLT	Lower level term
IQRMP	Integrated Quality and Risk Management Plan
λ z	Terminal rate constant of the analyte in plasma
Max	Maximum
MedDRA	Medical Dictionary for Regulatory Activities
Min	Minimum
N	Number non-missing observations
P10	10th percentile
P90	90th percentile
po	Orally
PKS	Pharmacokinetic parameter analysis set
Q1	1st quartile
Q3	3rd quartile

---

Term	Definition / description
qd	Once daily
R	Reference treatment
RAGe	Report Appendix Generator system
REP	Residual effect period
Rifa	Rifampicin
SD	Standard deviation
SOC	System organ class
T	Test treatment
TS	Treated set
ULN	Upper limit of normal
WHO-DD	World Health Organization Drug Dictionary
XPKISTAT	Library of SAS ® Macros for PK analysis

### **3. INTRODUCTION**

As per ICH E9 ([1](#)), the purpose of this document is to provide a more technical and detailed elaboration of the principal features of the analysis described in the protocol, and to include detailed procedures for executing the statistical analysis of the primary and secondary variables and other data.

This Trial statistical analysis plan (TSAP) assumes familiarity with the Clinical Trial Protocol (CTP). In particular, the TSAP is based on the planned analysis specification as written in CTP Section 7 “Statistical Methods and Determination of Sample Size”. Therefore, TSAP readers may consult the CTP for more background information on the study, e.g., on study objectives, study design and population, treatments, definition of measurements and variables, planning of sample size, randomisation.

Study data (including data entered in the RAVE EDC system and external data provided by suppliers) will be stored in a Clinical Data Repository (CDR).

Pharmacokinetic (PK) parameters will be calculated using Phoenix WinNonlinTM software (version 6.3 or higher, Certara USA Inc., Princeton, NJ, USA).

The statistical analyses will be performed within the validated working environment CARE, including SASTM (current Version 9.4, by SAS Institute Inc., Cary, NC, USA), and a number of SASTM-based tools (e.g., macros for the analyses of AE data or laboratory data; Report Appendix Generator system (RAGe) for compilation/formatting of the CTR appendices).

#### **4. CHANGES IN THE PLANNED ANALYSIS OF THE STUDY**

All analyses as planned in the CTP will be performed and are described in more detail in this TSAP.

## 5. ENDPOINTS

The pharmacokinetic parameters listed in Section 2.1 of the CTP for drug BI 894416 will be calculated according to the BI Standard Operating Procedure (SOP) 'Standards and processes for analyses performed within Clinical Pharmacokinetics/Pharmacodynamics' [001-MCS-36-472] (7).

### 5.1 PRIMARY ENDPOINTS

#### Section 2.1.2 of the CTP:

*The following pharmacokinetic parameters will be determined for BI 894416:*

- $AUC_{0-\infty}$  (area under the concentration-time curve of the analyte in plasma over the time interval from 0 extrapolated to infinity)
- $C_{max}$  (maximum measured concentration of the analyte in plasma)

### 5.2 SECONDARY ENDPOINTS

#### 5.2.1 Key secondary endpoints

This section is not applicable as no key secondary endpoints have been defined in the CTP.

#### 5.2.2 Secondary endpoints

#### Section 2.1.3 of the CTP:

*The following pharmacokinetic parameter will be determined for BI 894416:*

- $AUC_{0-tz}$  (area under the concentration-time curve of the analyte in plasma over the time interval from 0 to the last quantifiable data point)

### **5.3.2 Safety endpoints**

**Section 2.2.2.2 of the CTP: Safety and tolerability of BI 894416 will be assessed based on:**

- *Adverse events (including clinically relevant findings from the physical examination)*
- *Safety laboratory tests*
- *12-lead ECG*
- *Vital signs (blood pressure, pulse rate)*

## **6. GENERAL ANALYSIS DEFINITIONS**

### **6.1 TREATMENTS**

For basic study information on investigational products, assignment of treatment sequences and selection of doses, please see CTP, Sections 3 and 4.

The study will be performed as an open-label trial with two treatments (T and R) and one fixed sequence (R then T).

In total, it was planned to assign 16 healthy male subjects.

For details of dosage and formulation see Table 6.1: 1 below:

Table 6.1: 1 Treatments and labels used in the analysis

Treatment	Short label
R BI 894416, 2*25 mg tablet, po, qd	BI
T BI 894416, 2*25 mg tablet, qd + rifampicin, 600 mg tablet, qd	BI+Rifa

**Section 1.2.3 of the CTP:** *The Residual Effect Period (REP, i.e., the period after the last dose with measurable drug levels and/or pharmacodynamic effects still likely to be present) of BI 894416 has not been defined yet. [...] For the use of rifampicin in this trial, the REP is defined as 6 days.*

The following separate study phases will be defined for the analyses of AEs:

Table 6.1: 2 Flow chart of analysis phases for statistical analyses of AEs

Study analysis phase	Label	Start (inclusive)	End (exclusive)
Screening	Screening	Date of informed consent	Date/time of administration of BI 894416 in treatment period 1
On-treatment	BI	Date/time of administration of BI 894416 in treatment period 1	Date/time of first administration of rifampicin in treatment period 2
On-treatment	Rifa	Date/time of first administration of rifampicin in treatment period 2	Date/time of administration of BI 894416 in treatment period 2
On-treatment	BI+Rifa	Date/time of administration of BI 894416 in treatment period 2	0:00h on the day after EoT visit

**Section 7.3.4 of the CTP:** *Note that AEs occurring after the last per protocol contact but entered before final database lock will be reported to Pharmacovigilance only and will not be captured in the trial database.*

Please note that all AEs reported between start of trial drug administration and the last per-protocol contact will be considered on treatment.

The following AE displays will be provided in the report:

Section 15.3 and Appendix 16.1.13.1.8 (for ClinicalTrials.gov and EudraCT only) of the CTR displays:

In these displays, the on-treatment phase will be analysed (labelled with the name of the study treatment (short label)). Screening period will not be included in this analysis.

The following totals will be provided in addition (Section 15.3 only):

- a total over all on-treatment phases involving BI ("BI Total on treatment")
- a total over all on-treatment phases included in this analysis ("Total on treatment")

In Section 15.4 and Appendix 16.2 (Listings) of the CTR displays screening will be included and no totals will be provided.

Tables of vital signs and laboratory values will present results by the above mentioned on treatment phases apart from "Rifa" treatment.

For detailed information on the handling of the treatments refer to Technical TSAP ADS (analysis data set) plan and Data Reviewers guide.

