### **1.2.3 Residual Effect Period**

The Residual Effect Period (REP, i.e., the period after the last dose with measurable drug levels and/or pharmacodynamic effects still likely to be present) of BI 894416 has not been defined yet. However, the elimination half-life of BI 894416 is short (gMean terminal half-life between 2.96 and 5.31 h in the SRD part of trial 1371-0001), the mode of action is reversible, and safety and tolerability in previous trial 1371-0001 were good. This suggests that the occurrence of any potential adverse effects would likely be of short duration (i.e. few days). When given together with rifampicin, it is expected that plasma exposure of BI 894416 could be decreased as a result of CYP enzyme and/or P-glycoprotein induction and the time of relevant plasma exposure could be shortened. An increase of BI 894416 plasma exposure when given with rifampicin in this trial is not expected.

The follow-up visit is earliest on Day 8 following BI 894416 dosing in period 2, as this is expected to cover the period in which any potential adverse effects could reasonably occur.

For the use of rifampicin in this trial, the REP is defined as 6 days.

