#### 1.4.3.3 Risks related to combined administration of BI 894416 and rifampicin

##### Potential effects of BI 894416 on rifampicin pharmacokinetics and side effects

The last dose of rifampicin will be given 14 hours prior to BI 894416 in period 2. In this trial, no relevant effect of BI 894416 on rifampicin pharmacokinetics or side effects is expected.

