### 3. DESCRIPTION OF DESIGN AND TRIAL POPULATION

#### 3.1 OVERALL TRIAL DESIGN AND PLAN

The study will be performed as an open-label, two-treatment, two-period, one-way crossover trial in healthy male subjects in order to compare the test treatment (T) to the reference treatment (R). The treatments will be one oral single dose of 50 mg BI 894416 as tablet formulation (tablet strength: 25 mg) following 7 days of pre-treatment with 600 mg rifampicin q.d. as tablet formulation (tablet strength: 600 mg) (T) and one oral single dose of 50 mg BI 894416 as tablet formulation (tablet strength: 25 mg) given alone (R). In both treatments, BI 894416 is administered in the fasting state. In the first treatment period (Period 1, Visit 2), all subjects are planned to undergo treatment R, and in the second treatment period (Period 2, Visit 3), all subjects are planned to undergo treatment T. For details, refer to Section [4.1](#).

There will be a washout period of at least 10 days between the administrations of BI 894416.

Based on the good safety and tolerability of BI 894416 in trial 1371-0001, the acceptable safety and tolerability of rifampicin in healthy volunteers and the fact that a decrease of BI 894416 exposure is expected when given together with the CYP and P-glycoprotein inducer rifampicin, it is acceptable to treat all subjects entered in this trial in a single cohort, i.e. with Day 1 of each treatment period on the same calendar day.

An overview of all relevant trial activities is provided in the [Flow Chart](#). For visit schedule and details of trial procedures at selected visits, refer to Sections [6.1](#) and [6.2](#), respectively.

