#### 4.1.4 Drug assignment and administration of doses for each subject

This trial is a one-way crossover study. All subjects will receive the 2 treatments in fixed order. The treatments to be evaluated are outlined in Table [4.1.4: 1](#) below.

Table 4.1.4: 1 Dosage and treatment schedule

Treatment period	Treatment	Substance	Formulation	Unit strength	Dosage	Total dose
1	R (Reference)	BI 894416	Tablet	25 mg	2 tablets as single dose on Day 1	50 mg
2	T (Test)	Rifampicin	Film-coated tablet	600 mg	1 tablet q.d on Days -7 to -1	4200 mg
		BI 894416	Tablet	25 mg	2 tablets as single dose on Day 1	50 mg

Administration of BI 894416 will be performed after subjects have fasted overnight; fasting is to start no later than 10 h before the scheduled dosing.

For administrations of rifampicin, subjects are advised to fast for at least 2 hours before and at least 30 minutes after drug administrations.

The investigator (or authorised designee) will administer the trial medication as an oral dose together with about 240 mL of water to subjects who are in a standing position. For drug administration, the so-called four-eye principle (two-person rule) should be applied. For this, one authorised employee of the trial site should witness the administration of trial medication, and – if applicable – its preparation (e.g. reconstitution), if correct dosage cannot be ensured otherwise.

For restrictions with regard to diet, see Section [4.2.2.2](#).

Subjects will be kept under close medical surveillance until 24 h after BI 894416 administration. During the first 4 h after BI 894416 administration, subjects are not allowed to lie down (i.e. no declination of the upper body of more than 45 degrees from upright posture).

The first rifampicin administration will be followed by a 2-hour post-administration in-house observation period.

The administrations of BI 894416 will be separated by a wash-out phase of at least 10 days.

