### 7.3.4 Safety analyses

Safety will be analysed based on the assessments described in Section [2.2.2.2](#). All treated subjects (TS, refer to Section [7.2](#)) will be included in the safety analysis. Safety analyses will be descriptive in nature and based on BI standards. No hypothesis testing is planned.

For all analyses, the treatment actually administered (= treatment at onset) to the subject will be used (any deviations from the randomised treatment will be discussed in the minutes of the Report Planning Meeting).

Treatments will be compared in a descriptive way. Tabulations of frequencies/proportions will be used to evaluate categorical (qualitative) data, and tabulations of descriptive statistics will be used to analyse continuous (quantitative) data.

Measurements (such as ECG, vital signs, or laboratory parameters) or AEs will be assigned to treatments (see Section [4.1](#)) based on the actual treatment at the planned time of the measurement or on the recorded time of AE onset (concept of treatment emergent AEs). Therefore, measurements planned or AEs recorded prior to first intake of trial medication in period 1 will be assigned to the screening period, those between treatment with BI 894416 in period 1 and first treatment with rifampicin in period 2 are attributed to the treatment interval “BI 894416 alone”, those between first treatment with rifampicin in period 2 and treatment with BI 894416 in period 2 are attributed to the treatment interval “rifampicin alone” and those occurring between treatment with BI 894416 in period 2 and the individual subject’s end of trial are attributed to the treatment interval “BI 894416 + rifampicin”. These assignments including the corresponding time intervals will be defined in detail in the TSAP. Note that AEs occurring after the last per protocol contact but entered before final database lock will be reported to Pharmacovigilance only and will not be captured in the trial database.

Additionally, further treatment intervals (analysing treatments) may be defined in the TSAP in order to provide summary statistics for time intervals, such as combined treatments, on-treatment totals, or periods without treatment effects (such as screening and follow-up intervals).

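### AE incidence is compared across phases whose lengths differ and depend on scheduling (BI at least 82 h, BI+Rifa 184 to 352 h), so the raw percentages are not like for like

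*SAP*

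**What the plan says.** SAP 6.1, Table 6.1: 2, defines three on-treatment phases for AEs:

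- **BI** starts at the Period 1 dose of BI 894416 and ends at "Date/time of first administration of rifampicin in treatment period 2".
- **Rifa** runs from there to the Period 2 dose of BI 894416.
- **BI+Rifa** runs from that dose to "0:00h on the day after EoT visit".

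The same section treats every AE up to the last planned contact as on treatment, and defines no follow-up phase. SAP 7.8.1 bases the AE tables on how many subjects had an event, by treatment. Neither document plans a rate per unit of time or a matched post-dose window for AEs. On the use of these tables, Protocol 7.3.4 says "Treatments will be compared in a descriptive way".

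The phase lengths follow from the schedule. Protocol 3.1 states: "There will be a washout period of at least 10 days between the administrations of BI 894416". Protocol 4.1.4 repeats the 10-day minimum, and neither section gives a maximum. The Flow Chart puts the first rifampicin dose at -158:00 relative to BI 894416 and the end-of-trial visit on Day 8 to 15. Protocol 1.2.3 confirms the lower end: "The follow-up visit is earliest on Day 8 following BI 894416 dosing in period 2".

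**The concern.** A count of subjects with at least one event grows with observation time. Two columns are like for like only if they cover comparable time after dosing, or if time is allowed for. Here the BI column stops when rifampicin starts, while the BI+Rifa column continues to the end-of-trial visit.

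Ascertainment differs as well. For a subject who completes both periods, the end-of-trial laboratory, ECG, neurological and physical checks fall only in BI+Rifa. Clinically relevant findings from them become AEs (Protocol 5.2.5.1 and 5.2.6.1.1).

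Safety is a further objective (Protocol 7.1), and no test or model is planned for it. The side-by-side percentages are therefore the AE comparison. The same on-treatment phases feed the registry displays (SAP 6.1). A difference produced by the calendar could be read as an effect of the combination, or could hide one.

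**Working it through.** **Inputs.** Last rifampicin dose: "The last dose of rifampicin will be given 14 hours prior to BI 894416 in period 2" (Protocol 1.4.3.3). There are seven daily doses (Protocol 4.1.4). The minimum gap between BI 894416 doses is 10 days = 240 h (Protocol 3.1). BI 894416 is given at about 08:00 on Day 1, and the end-of-trial visit is on Day 8 to 15 (Flow Chart). N = 16.

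**Reproducing the plan's figure.** First rifampicin dose = -14 - 6 × 24 = -158 h, which matches the Flow Chart.

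**Phase lengths.**

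- BI = gap - 158 h. At 10 days: 240 - 158 = 82 h. At 14 days: 336 - 158 = 178 h. At 21 days: 504 - 158 = 346 h. At 22 days: 528 - 158 = 370 h.
- Rifa = 158 h.
- BI+Rifa, end of trial on Day 8: 16 + 7 × 24 = 184 h. On Day 15: 16 + 14 × 24 = 352 h.
- Ratio to the shortest BI phase: 184/82 = 2.2 and 352/82 = 4.3. At a 14-day gap: 184/178 = 1.0 and 352/178 = 2.0.
- Equal lengths need a gap of (184 + 158)/24 = 14.25 days (Day 8) or (352 + 158)/24 = 21.25 days (Day 15). With a longer gap, BI is the longer phase.

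**Against the plan's own residual effect period.** Protocol 1.2.3 states: "For the use of rifampicin in this trial, the REP is defined as 6 days". That period ends at -14 + 144 = 130 h after the Period 2 BI 894416 dose. BI+Rifa continues for a further 184 - 130 = 54 h to 352 - 130 = 222 h.

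**Illustration.** The documents give no background AE rate. Assume a constant hazard, no drug effect and independent phases. If p is the incidence in 82 h, the incidence in t hours is 1 - (1 - p)^(t/82). For p = 10%: 1 - 0.9^(184/82) = 21% and 1 - 0.9^(352/82) = 36%. The last column compares two binomial counts with n = 16.

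| Assumed incidence in 82 h (BI, 10-day gap) | BI+Rifa, 184 h | BI+Rifa, 352 h | Chance BI+Rifa shows strictly more subjects |
|---|---|---|---|
| 5% | 10.9% | 19.8% | 61% to 85% |
| 10% | 21.1% | 36.4% | 74% to 95% |
| 20% | 39.4% | 61.6% | 85% to 99% |
| 30% | 55.1% | 78.4% | 90% to over 99% |

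In the 10% row the expected counts are 1.6 subjects in BI against 3.4 to 5.8 in BI+Rifa.

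**Reversal.** With the same 10% assumption, a 21-day gap and end of trial on Day 8, BI lasts 346 h and BI+Rifa 184 h. The expected incidences are 36% and 21%, and the chance that BI+Rifa shows more subjects is 13%.

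**The case against.** A reader might infer that the combination will show more AEs. The documents do not support that. The 82 h is a floor, the gap has no upper limit, and a long enough gap reverses the expected direction. Even at 10 days the excess is an expectation in 16 subjects, not a certainty.

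A reader might also infer that the whole safety comparison is biased. It is not. Laboratory values and vital signs are summarised by planned time point with change from baseline (SAP 7.8.2 and 7.8.3), so those summaries do not depend on phase length.

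Other arguments carry weight:

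- **Constant hazard is an assumption that gives phase length a large role.** BI 894416 has a reported half-life of 2.96 to 5.31 h, and Protocol 1.2.3 expects any adverse effects to be brief. Every planned BI phase covers at least 82 h, about 15 half-lives at 5.31 h (82/5.31 = 15.4). Events that cluster soon after dosing would be caught in both phases.
- **Scheduled questioning does not rise in proportion to hours.** Both periods have the in-house stay and the 34 h and 48 h visits. BI+Rifa then adds the end-of-trial contact.
- **The phases are prespecified.** Protocol 7.3.4 sets the same intervals. Keeping late events on treatment is cautious for attribution, since Protocol 1.2.2 says induction may take roughly two weeks to wear off.
- **Matching the windows would not isolate the combination.** Rifampicin's own AEs and the fixed order of periods would still be mixed in.

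The first two points limit the size of the problem, and the third is a reason to keep the existing table. None makes the two percentages comparable. Protocol 7.3.4 also lets the analysis plan add intervals, including follow-up, so a supplementary table is within its terms.

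**Conclusion.** The concern holds for the descriptive AE comparison. Subjects with AEs are counted over phases of unequal length, and the length of the BI phase is left partly to scheduling. At or near the minimum gap, BI+Rifa is observed 2.2 to 4.3 times as long and alone contains the end-of-trial examination. Its raw incidence is then expected to be higher without any rifampicin effect. At gaps of 14.25 days (end of trial on Day 8) to 21.25 days (Day 15) the lengths are equal, and beyond that the expected direction reverses.

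The phase lengths rest only on the documents and clock arithmetic. The incidence figures rest on an assumed background rate, a constant hazard and independent phases, and would be smaller if events cluster early. Protocol 3.1 allows all subjects to be dosed as one cohort on the same days. If that is done, all share one dose gap, and the imbalance does not average out across subjects.

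The pharmacokinetic endpoints are untouched. This is a worthwhile, low-cost improvement to the safety reporting and does not threaten the trial's main conclusion.

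**What to change.** Keep Table 6.1: 2 for the standard displays. Add to SAP 6.1 and 7.8.1 one AE frequency table by treatment, limited to the same window after the BI 894416 dose in each period. The window could be 0 to 82 h, the shortest BI phase the planned schedule allows, or dosing to the 48 h visit. Assign events by onset time, as the SAP already does, with subjects dosed in that period as the denominator. State that any BI versus BI+Rifa comparison of AEs in the report rests on this table, and note beside it that rifampicin's own AEs and period effects remain confounded with the combination.

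A fixed window is preferable to a rate per subject-day here, because it does not rely on the constant hazard questioned above.

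The cost is a short SAP addition and one table from onset times already recorded (Protocol 5.2.6.2.1). The drawback is that later events appear only in the full-phase tables.
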